### 3 HYPOTHESES, OBJECTIVES, AND ENDPOINTS

Hypothesis testing will not be performed in this protocol.

All objectives and endpoints apply to Japanese participants with Mature B-cell neoplasms who have failed or are intolerant to previous treatment:

Primary Objective	Primary Endpoint
To evaluate the safety and tolerability of treatment with nemtabrutinib	Dose limiting toxicities (DLTs) Adverse events (AEs) Discontinuing study treatment due to AEs
Secondary Objectives	Secondary Endpoints
To evaluate the PK profile of nemtabrutinib	PK parameters including AUC, Cmax, Tmax and Cmin in plasma
To evaluate objective response rate (ORR) and duration of response (DOR) following administration with nemtabrutinib for Chronic Lymphocytic Leukemia (CLL)/Small Lymphocytic Lymphoma (SLL) participants per iwCLL criteria 2018, for Waldenström's Macroglobulinemia (WM) /Lymphoplasmacytic lymphoma (LPL) participants per International Workshop on WM (IWWM) 2014 and for mature B-cell neoplasms participants other than CLL/SLL/WM/LPL per Lugano criteria 2014 as assessed by investigator	CLL/SLL participants: - Objective response (OR): complete response (CR), or complete response with incomplete bone marrow recovery (CRi), or nodular partial response (nPR), or partial response (PR) WM/LPL participants: - OR: CR, very good partial response (VGPR), or PR Mature B-cell neoplasms participants other than CLL/SLL/WM/LPL: - OR: CR or PR All participants: - DOR, defined as the time from the first documented evidence of an objective response until disease progression or death due to any cause, whichever occurs first
Tertiary/Exploratory Objectives	Tertiary/Exploratory Endpoints
For CLL/SLL participants:  To evaluate the ORR including response category of partial response with lymphocytosis (PRL) following administration with nemtabrutinib per iwCLL criteria 2018 as assessed by investigator	Objective response including PRL, defined as CR, CRi, nPR, PR, or PRL

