- Physical findings – Symptomatic or bulky ( $\geq 5$  cm in the longest diameter) lymphadenopathy, symptomatic hepatomegaly, and/or symptomatic splenomegaly.
- Laboratory abnormalities – Hemoglobin  $< 10$  g/dL or platelet count  $< 100,000/\text{microL}$ .
- Coexisting disease – Immunoglobulin light chain amyloidosis with organ dysfunction, symptomatic cryoglobulinemia, cold agglutinin anemia, immune hemolytic anemia and/or thrombocytopenia, or nephropathy due to WM/LPL.

4. WM/LPL participants:

Have measurable disease, satisfying any of the following for participants with WM/LPL

- At least 1 lesion that can be accurately measured in at least 2 dimensions with spiral CT scan (minimum measurement must be  $> 15$  mm in the longest diameter or  $> 10$  mm in the short axis)
- IgM  $\geq 450$  mg/dL
- bone marrow infiltration of  $\geq 10\%$ .

5. Participants with B-cell malignancies except CLL/SLL/WM/LPL:

Have measurable disease defined as at least 1 lesion that can be accurately measured in at least 2 dimensions with spiral CT scan, except the participants with CLL/SLL/WM/LPL. A minimum measurement must be >15 mm in the longest diameter or >10 mm in the short axis.

6. Performance status of 0-2 on the ECOG Performance Scale within 7 days prior to allocation.

7. Have a life expectancy of at least 3 months, based on the investigator assessment.

8. Have the ability to swallow and retain oral medication.

9. Participants who are HBsAg positive are eligible if they have received HBV antiviral therapy for at least 4 weeks and have undetectable HBV viral load prior to the first dose of study intervention.

Note: Participants should remain on antiviral therapy throughout study intervention and follow local guidelines for HBV antiviral therapy post completion of study intervention.

Hepatitis B screening tests are not required unless:

- Known history of HBV infection
- As mandated by local health authority

10. Participants with history of HCV infection are eligible if HCV viral load is undetectable at screening.

Note: Participants must have completed curative antiviral therapy at least 4 weeks prior to the first dose of study intervention.

Hepatitis C screening tests are not required unless:

- Known history of HCV infection
- As mandated by local health authority

11. Adequate organ function as defined in [Table 3](#). Specimens must be collected within 7 days prior to the start of study intervention.

Table 3 Adequate Organ Function Laboratory Values

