### 9.4.2 Efficacy Endpoints

- Objective Response (OR)

OR is defined as participants who achieve at least a PR, per disease-specific criteria (see Section 8.2.1) as assessed by investigator. Objective response rate (ORR) is the proportion of participants in the analysis population with objective response.

- Duration of Response (DOR)

For participants who demonstrate an objective response as assessed by investigator, per disease-specific criteria, duration of response is defined as the time from the first documented evidence of an objective response until disease progression or death due to any cause, whichever occurs first.

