#### **10.9.3.2.2 Post-baseline Assessment**

##### **Target lesions**

At each follow up visit, target, non-target lesions and the presence of new lesions in images will be assessed to provide a collective lymph node response.

- Complete Response (CR): All target lymph nodes must have regressed to normal size defined as  $\leq 1.5$  cm in LDi. Target extranodal sites must be absent (0 by 0 cm).

- Partial Response (PR):  $\geq 1\%$  decrease in SPD of target lesions from baseline, and no individual lesion meets the criteria for progression.
- Progressive Disease (PD): Target lesion progression is based on either a  $\geq 50\%$  increase in the SPD of all target lesions, or a  $\geq 50\%$  increase in the LDi of any single target lesion from its nadir (smallest size previously seen, which can include the baseline if that is the smallest), which meets all of the following requirements
  - The final size of the individual lesion must be  $> 1.5$  cm in LDi
  - And one of the following:
    - For lesions  $< 2$  cm at nadir, the lesion's LDi must have increased by  $\geq 0.5$  cm at the current timepoint from its nadir.
    - For lesions  $\geq 2$  cm at nadir, the lesion's LDi must have increased by  $\geq 1$  cm at the current timepoint from its nadir.
- Stable Disease (SD): A target lesion assessment of SD requires all of the following:
  - Target lesions do not meet the criteria for CR or PR
  - No individual lesion meets the criteria for progression
- Not Evaluable (NE): When any target lesion identified at baseline cannot be evaluated at a post-baseline timepoint due to missing imaging, poor image quality, changes in the lesion or background that precludes assessment, or focal therapy or other procedures that change the lesion size, the target lesion assessment will be NE, unless progression is identified in another target lesion.

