### **Radiology Response**

Target	Non-target	New lesions	Spleen Response	Radiology Response
CR	CR	No	CR	CR
CR	SD	No	PR/CR	PR
PR	CR/SD	No	PR/CR	PR
PR	CR/SD	No	SD	SD
SD	CR/SD	No	Any but PD	SD
Any non-PD	NE	No	Any but PD	NE
NE	Any non-PD	No	Any but PD	NE
Any non -PD	Any non-PD	No	NE	NE
PD	Any	Yes/No	Any	PD
Any	PD	Yes/No	Any	PD
Any	Any	Yes	Any	PD
Any	Any	Yes/No	PD	PD
NA	NA	No	Normal (CR)	NED
Abbreviations: CR=complete response; NA=not applicable; NE=not evaluable; NED=no evidence of disease; PD=progressive disease; PR=partial response; SD=stable disease. NA – No lesions of this type present at baseline. NED – No lesions of any kind seen at baseline, and none present at visit being evaluated.				

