#### Response category definitions

#### Overall Timepoint Assessment

Response and Sub-categories for assessment	Overall Timepoint Assessment
Complete Response (CR)	Complete resolution of disease (all of the following)
Serum IgM	CR (Normal Serum IgM from baseline)
Serum M-Protein Immunofixation	Negative If immunofixation status is not reported/not interpretable for any available timepoints, the best possible response is VGPR. One negative immunofixation is sufficient to be called CR for a particular visit. Once a negative immunofixation has been reported for a visit, any subsequent visits with immunofixation status not reported or not interpretable can be CR as long as all remaining data supports a continued CR status.
Extramedullary Disease by Physical Examination	No EMD Present
Cryoglobulinemia	
 
Negative cryoglobulinemia if cryoglobulinemia was Positive at baseline.
 
If cryoglobulinemia was negative or not available at baseline, a negative cryoglobulinemia assessment at post-baseline is not required for an overall timepoint assessment of CR.
 

Radiology Overall Response	CR or NED
Bone Marrow	Negative Negative assessment of bone marrow is required to confirm CR even if bone marrow is negative at baseline. Once a CR has been confirmed by bone marrow then repeat bone marrow is not required.
Other Confounding Factors	No If amyloidosis was present at baseline, then it must be absent. No new symptomatic disease should be observed.
Very Good Partial Response	At least one sub-category does not meet the criteria for CR; none of the sub-categories meet the criteria for PD; and responses are described below:
Serum IgM	VGPR or CR ( $\geq 90\%$ reduction in Serum IgM or normal from baseline)
Radiology Overall Response	CR or PR
Extramedullary Disease by Physical Examination	
 
Spleen and/or Lymph nodes which were assessed as Enlarged at baseline are assessed as Normal/Not Enlarged or
 
No EMD is present at baseline and post-baseline
 

New Symptomatic Disease	Absent

Response and Sub-categories for assessment	Overall Timepoint Assessment
Partial Response	All criteria have to met
Serum IgM	PR ( $\geq 50\%$ and $< 90\%$ reduction in Serum IgM from baseline)

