Extramedullary Disease by Physical Examination	
 
Spleen and/or Lymph nodes which were assessed as Enlarged at baseline are assessed as Normal/Not Enlarged or
 
No EMD is present at baseline and post-baseline
 

Radiology Overall Response	
 
Any but PD
 

New Symptomatic Disease	Absent
Minor Response	No new signs of active disease or progression
Serum IgM	MR ( $\geq 25\%$ and $< 50\%$ reduction in Serum IgM from baseline)
Extramedullary Disease by Physical Examination	
 
Spleen and/or Lymph nodes which were assessed as 'Enlarged at baseline' are assessed as 'Normal/Not Enlarged' or 'Enlarged – Reduction from baseline' or
 
No EMD is present at baseline and post-baseline
 

Radiology Overall Response	
 
Any but PD
 

New Symptomatic Disease	Absent
Stable Disease	Not meeting the criteria for CR, VGPR, PR, MR, PD, NE or NED
Progressive Disease (PD)	Any of the categories meet the criteria for progression
Serum IgM	
 
PD unconfirmed, or
 
PD confirmed if serum IgM is the only indicator of PD (<math>\geq 25\%</math> in serum IgM from nadir)
 
Absolute increase of <math>> 5</math> g/L is required when increase of IgM is the only applicable criterion
 

Extramedullary Disease by Physical Examination	
Either spleen or lymph nodes are assessed as 'Enlarged New/recurrent' or 'Enlarged- Unequivocal Progression'
 
Progression due to lymph node/spleen enlargement by PE only should be unequivocal, and cannot drive progressive disease unless supported by other data (eg, IgM meets the criteria for PD as defined above)

Radiology Overall Response	PD
Bone Marrow	Positive (New or recurrent involvement in bone marrow associated with WM)
New Symptomatic Disease	Yes
Not evaluable	NE require AT LEAST ONE of the following, and no evidence of PD
Serum IgM	
Not available/evaluable or
 
All available IgM values are confounded by plasmapheresis

Extramedullary Disease by Physical Examination	Spleen and/or Lymph nodes were assessed as Enlarged at baseline and follow-up assessments are not performed
Radiology Overall Assessment	NE

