Cryoglobulinemia	If cryoglobulinemia is present, the overall tumor response can be NE based on the independent reviewer's oncological judgment.
New lesions	None

Response and Sub-categories for assessment	Overall Timepoint Assessment
No Evidence of Disease (NED)	All criteria have to be met
Serum IgM	Serum IgM or Serum M-Protein SPED was assessed as Normal at baseline and CR at Post-baseline
Extramedullary Disease by Physical Examination	No EMD at baseline and Post-baseline
Radiology Overall Assessment	NED
Bone Marrow	Negative at baseline and post-baseline
New Symptomatic Disease	None
Abbreviations: CR=complete response; EMD=extramedullary disease; IgM=immunoglobulin M; MR=minor response; NA=not applicable; NE=not evaluable; NED=no evidence of disease; PD=progressive disease; PE=physical examination; PR=partial response; SPED=serum protein electrophoresis; VGPR=very good partial response; WM=Waldenström's macroglobulinemia.	

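### In the WM/LPL response table, a participant short of CR with a 90% or greater IgM fall and radiology SD (or, read literally, NED) is graded SD, although a 50–89% fall is graded PR

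*Combined protocol and SAP*

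**What the plan says.** Section 3 counts three categories as response in WM/LPL: "OR: CR, very good partial response (VGPR), or PR". Section 9.4.2 adds that "OR is defined as participants who achieve at least a PR, per disease-specific criteria". Section 8.2.2 evaluates ORR separately by disease cohort, and Section 8.2.1.3 refers to Appendix 9 for the definitions.

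In the overall timepoint table of Section 10.9.3.3:

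- **CR** accepts radiology CR or NED. It also needs normal IgM, negative immunofixation, negative marrow and the remaining CR rows.
- **VGPR** needs an IgM fall of at least 90% or a normal IgM, radiology CR or PR, and either no extramedullary disease (EMD) on examination or its resolution.
- **PR** has the IgM condition "PR ( $\geq 50\%$ and $< 90\%$ reduction in Serum IgM from baseline". Radiology may be anything but PD, and the examination condition is the same as for VGPR.
- **MR** needs an IgM fall of at least 25% and under 50%.
- **SD** is the remainder: "Not meeting the criteria for CR, VGPR, PR, MR, PD, NE or NED".

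Section 10.9.3.2.2 defines radiology NED as "No lesions of any kind seen at baseline, and none present at visit being evaluated". Its target-lesion PR needs a 1% or greater "decrease in SPD of target lesions from baseline, and no individual lesion meets the criteria for progression". The spleen uses a 1% threshold too.

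**The concern.** Response grades should not get worse as IgM falls further. Here the PR and VGPR rows do not meet. PR stops just below a 90% fall, and VGPR starts at 90% but adds a radiology condition that PR does not have. A participant who passes 90% without meeting that condition has no response category left and drops to SD, which is a non-response. ORR and DOR in WM/LPL are secondary endpoints built on this table.

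A second, narrower question concerns the word *normal* in the VGPR IgM row. It carries no minimum fall and no requirement that IgM was raised at baseline. Together with a 1% radiology threshold, it could let a trivial change in node size decide a VGPR.

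**Working it through.** The plan states no figure on this point, so there is none to reproduce. The check applies the radiology and overall-response tables as written.

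**1. The gap at 90%.** Take a participant with no EMD on examination, IgM still above normal (so not CR), and no sign of progression.

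| IgM fall | Radiology PR | Radiology SD | Radiology NED |
|---|---|---|---|
| 49% | MR | MR | MR |
| 50% | PR | PR | PR |
| 89% | PR | PR | PR |
| 90% | VGPR | **SD** | **SD** |

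Radiology SD arises, for example, with unchanged target nodes, or with target PR and spleen SD.

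**2. How far the NED column depends on missing CR.** With radiology NED and a fall of 90% or 95%, there are eight combinations of IgM normal or not, immunofixation negative or not, and marrow negative or not. The result is SD in seven. It is CR in the one where all three hold, if the other CR rows are met.

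**3. From timepoint to endpoint.** The table grades visits, whereas OR is reaching at least PR. A participant with any visit graded PR, VGPR or CR is already a responder. ORR loses someone only if IgM moves directly to a fall of 90% or more and no visit earns one of those grades. If a 92% fall at week 12 is graded SD and the participant is graded CR at week 24, ORR is unaffected but DOR starts 24 − 12 = 12 weeks late.

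**4. Size.** Section 1.1 plans about 6 to 12 participants over all histologies and gives no WM/LPL number, so n is assumed. One participant moves ORR by 1/n. The exact 95% limits (Clopper-Pearson) for 0/n run from 0 to 1 − 0.025^(1/n); the lower limit for 1/n is 1 − 0.975^(1/n).

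| Assumed n | Shift in ORR | 95% CI at 0/n | 95% CI at 1/n |
|---|---|---|---|
| 3 | 33.3 points | 0 to 70.8% | 0.8 to 90.6% |
| 6 | 16.7 points | 0 to 45.9% | 0.4 to 64.1% |
| 12 | 8.3 points | 0 to 26.5% | 0.2 to 38.5% |

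An n of 12 would mean that every participant had WM/LPL. As a check on the interval routine only, it returns 42.4 to 69.3% for 32/57 and 19.7 to 61.5% for 9/23, the intervals printed in Section 2.2.2.3.

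**5. The normal-IgM route.** Section 5.1, item 4, says "Have measurable disease, satisfying any of the following for participants with WM/LPL", and the list includes a CT lesion or marrow infiltration alone, so raised IgM is not required under that item. The NED row shows that IgM normal at baseline can later be coded CR: "Serum IgM or Serum M-Protein SPED was assessed as Normal at baseline and CR at Post-baseline". Suppose IgM is normal, there is no EMD on examination (nodes seen only on CT) and the spleen is normal. A 1% fall in SPD then gives radiology PR and overall VGPR, even with a 0% or 10% IgM fall; unchanged nodes give SD. At a 50–89% fall the participant is PR anyway, so ORR changes only below 50%. If nodes remain enlarged on examination, VGPR is not reached.

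For scale, assume no true change and a normal measurement error in SPD change with SD 10%. One scan then shows a fall of at least 1% with probability P(Z < −1/10) = 46% (42% at SD 5%, 48% at SD 20%). This is conditional on all the circumstances just listed; it is not a rate of error in ORR.

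**The case against.** The strongest reply concerns participants without EMD. Section 10.9.3.1 says imaging need not be repeated for them and that imaging results are combined when applicable. The VGPR examination row admits participants with no EMD, and the CR row says that without an immunofixation result the best grade is VGPR. An investigator could reasonably skip the radiology row and grade VGPR. That reading is plausible for NED, although the table does not state it and its CR row names NED explicitly. It does not help a participant with radiology SD, so the gap stands there.

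A reader might infer that every 90% fall without EMD becomes SD. The documents do not support that, because such a participant is CR when all CR rows hold. Nor do they support saying that ORR is wrong in both directions: the undercount needs a direct move past 90% with no other qualifying visit.

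On the normal-IgM route, the reply is that WM/LPL is characterised by raised IgM (Section 2.2.1), that missing the 450 mg/dL entry route does not make IgM normal, and that *normal from baseline* can be read as normalisation. Those points make the route narrow and dependent on an ambiguous phrase. A reader might also call the 1% threshold a mistake, since the iwCLL and Lugano sections use 50%. But 1% is used for both nodes and spleen and may be a deliberate any-reduction rule; the documents cannot settle it.

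**Conclusion.** The gap is real as written. Short of CR, with radiology SD or (read literally) NED, an 89% IgM fall is PR and a 90% fall is SD. WM/LPL ORR can therefore be understated, and the start of DOR misdated, in the circumstances of steps 3 and 4 above. Any shift in ORR is conditional on an assumed number of WM/LPL participants, and there may be few or none.

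The normal-IgM and 1% route is a secondary ambiguity. It could add a false VGPR only where IgM is normal, its fall is under 50%, and EMD on examination is absent or resolved.

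This is a should-fix. ORR and DOR are secondary, no hypothesis is tested, and the DLT endpoint and dose-finding do not use this table.

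**What to change.** 1. In the PR row, change the IgM criterion to a reduction of 50% or more, not meeting CR or VGPR, with no upper limit. This alone closes the gap for both radiology SD and NED, and it is enough for ORR because PR and VGPR both count.
2. If NED is also added to the VGPR radiology row, to agree with the CR row and with VGPR's own examination row, define in the same change when normal IgM qualifies: abnormal at baseline and a stated minimum fall. Adding NED alone would turn a no-EMD participant short of CR, with a 30% fall into the normal range, from MR into VGPR. An abnormal-baseline condition without a minimum fall would not prevent this.
3. Confirm or justify the 1% threshold for nodes and spleen.
4. Re-derive any WM/LPL timepoint responses, ORR and DOR under the revised table.

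The cost is a wording change in Appendix 9 and re-derivation for whatever WM/LPL participants there are. No new data are needed.

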## 10.10 Appendix 10: Abbreviations

Abbreviation	Expanded Term
ABC	Activated B-cell
ADL	Activities of daily living
AE	Adverse event
AIHA	Autoimmune hemolytic anemia
ALT	Alanine aminotransferase
ANC	Absolute neutrophil count
APaT	All-Participants-as-Treated
aPTT	Activated partial thromboplastin time
AST	Aspartate aminotransaminase
ATP	Adenosine triphosphate
AUC	Area under the curve
AV	Atrial ventricular
BCL-6	B-cell lymphoma 6
BCR	B-cell receptor
BCRP	Breast cancer resistance protein
BM	Bone marrow
BSEP	Bile salt export pump
BTK	Bruton's tyrosine kinase
BTKi	BTK inhibitor
BUN	Blood urea nitrogen
CAR	Chimeric antigen receptor
CBC	Complete blood cell
CI	Confidence interval
CLL	Chronic lymphocytic leukemia
Cmax	Maximum concentration
Cmin	Minimum concentration
CMR	Complete metabolic response
CNS	Central nervous system
CONSORT	Consolidated Standards of Reporting Trials
CR	Complete response
CRF	Case Report Form
CRi	Complete response with incomplete bone marrow recovery
CrCl	Creatinine clearance

Abbreviation	Expanded Term
CSR	Clinical Study Report
CT	Computed tomography
CTCAE	Common Terminology Criteria for Adverse Events
CTFG	Clinical Trial Facilitation Group
CYP	Cytochrome P450
D	De-escalate to the next lower dose
DDI	Drug-drug interaction
DILI	Drug-induced liver injury
DL	Dose level
DLBCL	Diffuse large B-cell lymphoma
DLT	Dose-limiting toxicity
DNA	Deoxyribonucleic acid
DOR	Duration of response
DU	The current dose is unacceptably toxic
E	Escalate to the next higher dose
ECG	Electrocardiogram
ECI	Event of clinical interest
ECOG	Eastern Cooperative Oncology Group
eCRF	Electronic Case Report Form
EDC	Electronic data collection
EEA	European Economic Area
EMA	European Medicines Agency
EMD	Extramedullary disease
EOT	End of treatment
FDA	Food and Drug Administration
FDAAA	Food and Drug Administration Amendments Act
FDG	2 fluorodeoxyglucose
FISH	Fluoro in situ hybridization
FL	Follicular lymphoma
FLIPI	Follicular Lymphoma International Prognostic Index
FLIPI-2	Follicular Lymphoma International Prognostic Index-2
FSH	Follicle-stimulating hormone
GCB	Germinal center B-cell
GCP	Good Clinical Practice

Abbreviation	Expanded Term
GCSF	Granulocyte colony-stimulating factor
GFR	Glomerular filtration rate
HBsAg	Hepatitis B surface antigen
HBV	Hepatitis B virus
HCV	Hepatitis C virus
hERG	Human ether-à-go-go-related gene
Hgb	Hemoglobin
HIV	Human immunodeficiency virus
HRT	Hormone replacement therapy
IB	Investigator's Brochure
IC50	Half maximal inhibitory concentration
ICF	Informed Consent Form
ICH	International Council on Harmonisation
IEC	Independent Ethics Committee
Ig	Immunoglobulin
IgA/IgG/IgM	Immunoglobulin A, G, and M
IGHV	Immunoglobulin heavy chain variable region gene
INR	International normalized ratio
IPI	International Prognostic Index
IRB	Institutional review board
ISSWM	International Prognostic Scoring System for Waldenström Macroglobulinemia
IUD	Intrauterine device
IUS	Intrauterine hormone-releasing system
IV	Intravenous
iwCLL	International Workshop on Chronic Lymphocytic Leukemia
IWWM	International Workshop on Waldenström's macroglobulinemia
L	Liter(s)
LAM	Lactational amenorrhoea method
LDH	Lactate dehydrogenase
LDi	Longest diameter
LDT	Lymphocyte doubling time
LPL	Lymphoplasmacytic lymphoma
MCH	Mean corpuscular hemoglobin
MCL	Mantle-cell lymphoma

Abbreviation	Expanded Term
MCV	Mean corpuscular volume
MIPI	Mantle-cell Lymphoma International Prognostic Index
MIPI-c	Combined Mantle-cell Lymphoma International Prognostic Index
MOA	Mechanism of action
MR	Minor response
MRD	Minimal residual disease
MRI	Magnetic resonance imaging
mRNA	Messenger RNA
MTD	Maximum tolerated dose
mTPI	Modified Toxicity Probability Interval
MZL	Marginal zone lymphoma
N/n	Number
NA	Not applicable
NCI	National Cancer Institute
NE	Not evaluable
NED	No evidence of disease
NF-κB	Nuclear factor kappa-light chain-enhancer of activated B-cells
NHL	Non-Hodgkin's Lymphoma
nPR	Nodular partial response
NSAE	Nonserious adverse event
OME	Other important medical event
OR	Objective response
ORR	Objective response rate
OS	Overall survival
PB	Peripheral blood
PD	Progression disease
PD	Pharmacodynamics
PE	Physical examination
PET	Positron emission tomography
PFS	Progression-free survival
P-gp	P-glycoprotein
PK	Pharmacokinetic(s)
PMD	Progressive metabolic disease
PMR	Partial metabolic response

Abbreviation	Expanded Term
PO	Orally
PPD	Product of perpendicular diameters
PR	Partial response
PRL	Partial response with lymphocytosis
PT	Prothrombin time
PTT	Partial thromboplastin time
q12w	Every 12 weeks
QD	Once daily
QTc	QT interval corrected
QTcF	QT interval corrected using Fridericia's formula
RBC	Red blood cell
RNA	Ribonucleic acid
ROI	Region of interest
RP2D	Recommended Phase 2 dose
S	Stay at the current dose
SAE	Serious adverse event
SD	Stable disease
SDi	Short axis diameter
SLL	Small lymphocytic lymphoma
SMD	Stable metabolic disease
SoA	Schedule of activities
SPD	Sum of products of diameters
SPED	Serum protein electrophoresis
sSAP	Supplemental Statistical Analysis Plan
SUSAR	Suspected unexpected serious adverse reaction
TLS	Tumor lysis syndrome
UGT	Uridine-5'-diphospho-glucuronosyltransferase
ULN	Upper limit of normal
US	United states
VGPR	Very good partial response
WBC	White blood cell
WHO	World Health Organization
WM	Waldenström's macroglobulinemia
WOCBP	Woman/women of childbearing potential

